# 12.5 Study Monitoring Requirements

It is the responsibility of the Investigator to ensure that the study is conducted in accordance with the protocol, ICH GCP, and applicable regulatory requirements, and that valid data are entered into the eCRFs.

To achieve this objective, the CRA's duties are to aid the Investigator and, at the same time, the Sponsor, in the maintenance of complete, legible, well organized, and easily retrievable data. Before the enrollment of any subject in this study, the Sponsor or their designee will review with the Investigator and site personnel the following documents: protocol, Investigator's Brochure, eCRFs and procedures for their completion, informed consent process, and the procedure for reporting SAEs.

The Investigator will permit the Sponsor or their designee to monitor the study as frequently as deemed necessary to determine that data recording and protocol adherence are satisfactory. During the monitoring visits, information recorded on the eCRFs will be verified against source documents and requests for clarification or correction may be made. After the eCRF data is entered by the site, the CRA will review the data for safety information, completeness, accuracy, and logical consistency. Computer programs that identify data inconsistencies may be used to help monitor the clinical study. If necessary, requests for clarification or correction will be sent to Investigators. The Investigator and his/her staff will be expected to cooperate with the CRA and provide any missing information, whenever possible.

All monitoring activities will be reported and archived. In addition, monitoring visits will be documented at the investigational site by signature and date on the study-specific monitoring log.

#### 12.6 Disclosure of Data

Data generated by this study must be available for inspection by the Pharmaceutical and Medical Devices Agency, other applicable health authorities, the Sponsor or their designee, and the IRB/IEC as appropriate. Subjects or their legal representatives may request their medical information be given to their personal physician or other appropriate medical personnel responsible for their welfare.

A subject's medical information obtained during the study is confidential and disclosure to third parties other than those noted above is prohibited.

#### 12.7 Retention of Records

To enable evaluations and/or audits from regulatory authorities or the Sponsor, the Investigator will keep records, including the identity of all participating subjects (sufficient information to link records, e.g., eCRFs and hospital records), all original signed ICFs, copies of all eCRFs, SAE forms, source documents, and detailed records of treatment disposition. The records should be retained by the Investigator according to specifications in the ICH guidelines, local regulations, or as specified in the clinical study agreement, whichever is longer. The Investigator must obtain written permission from the Sponsor before disposing of any records, even if retention requirements have been met.

If the Investigator relocates, retires, or for any reason withdraws from the study, the Sponsor should be prospectively notified. The study records must be transferred to an acceptable designee, such as another Investigator, another institution, or to the Sponsor.

# 12.8 Publication Policy

Following completion of the study, the data may be considered for publication in a scientific journal or for reporting at a scientific meeting. Each Investigator is obligated to keep data pertaining to the study confidential. The Investigator must consult with the Sponsor before any study data are submitted for publication. The Sponsor reserves the right to deny publication rights until mutual agreement on the content, format, interpretation of data in the manuscript, and journal selected for publication are achieved.

# 12.9 Insurance and Indemnity

In accordance with the relevant national regulations, the Sponsor has taken out subject liability insurance for all subjects who have given their consent to the clinical study. This coverage is designed for the event that a fatality, physical injury, or damage to health occurs during the clinical study's execution.

# APPENDIX A: CORE PHASE SCHEDULE OF EVENTS

Phase	PE										(	Core F	Phase							
Period	Screen	BL		Titı	ration		Con		tant I Redu			tion		Ma	aintena	nce		Dose- Taper b	Follow- up b	- Unsch Visit c
Visits d	1	2	3	4	5, 6	7	8	9	10	11	12	13	14, 15	16, 17	18, 19	20, 21	EOT 22	23-26	27-30	_
Days	-28 to -1	1	5±1	8[contact]														
Weeks	-4			1	2-3	4	6	8	10	12	14	16	18, 19	20, 21	22, 23	24, 25	26	27-30	31-34	_
Informed consent	X																			
Demographics	X																			
Medical/surgical history, including ITP history	X																			
Height/Weight	X																			
Concomitant medications/procedures	X	X	X	X	X	X	X	X	X	X	X	X	X	X	X	X	X	X	X	X
Inclusion/Exclusion	X	X															Xe			
Vital signs	X	X	X	X	X	X	X	X	X	X	X	X	X	X	X	X	X	X	X	X
Physical examination	X	X		X		X			X			X		Xf			X		Xf	
Dispense study drug and diary, as needed		X	X	X	X	X	X	X	X	X	X	X	X	X	X	X	X	X		
Retrieve unused study medication and record compliance			X	X	X	X	X	X	X	X	X	X	X	X	X	X	X	X		
Concomitant ITP drug dose titration							X	X	X	X	X	X								
Platelet counts	Xg	Xg	X	X	X	X	X	X	X	X	X	X	X	X	X	X	X	X	X	X
Chemistry, Hematology and Coag	X	X		X					X			X					X		Xh	
PK blood sampling				Xi	$X^{j}$	$X^{i}$	Xi		$X^{j}$			Xi					$X^{i}$			
Pregnancy testing	X	X							X					X k			X		X k	
Adverse events	X	X	X	X	X	X	X	X	X	X	X	X	X	X	X	X	X	X	X	X
WHO Bleeding score		X	X	X	X	X	X	X	X	X	X	X	X	X	X	X	X	X	X	X

- BL = Baseline, EOT = End-of-Treatment, ITP = Immune Thrombocytopenia, PK = pharmacokinetic, PE = Pre-enrollment, Unsch = unscheduled, WHO = World Health Organization.
- a: Subjects requiring study drug dose adjustments, undergoing concomitant ITP medication reduction or those who receive rescue therapy during the Core Phase are required to return for weekly visits for 3 consecutive weeks.
- b: Dose-tapering and Follow-up Visits are for subjects who will not be entering the Extension Phase.
- c: This column details the minimum assessments required for those subjects who need an unscheduled visit for dose titration or additional platelet count blood draws, however additional assessments may be performed as required based on other reasons for the unscheduled visit.
- d: Visits scheduled on a weekly basis should occur within a +/- 2-day timeframe, except Day 5 this visit should occur within +/- 1 day and Day 8 this visit should occur within a +2-day window. Visits scheduled on an every 2-week basis should be within a +/- 3-day timeframe.
- e: At Visit 22 the inclusion/exclusion criteria for the Extension Phase should be reviewed to confirm subject eligibility for those subjects who are willing to enter the Extension Phase.
- f: The physical exam will be performed at Week 20 and Week 34.
- g: The Screening Visit and Day 1 Baseline Visit platelet count will be averaged to obtain the baseline platelet count value. The 2 samples must be obtained  $\geq$ 48 hours and  $\leq$ 2 weeks apart and the results must be available prior to enrollment. Therefore, an additional screening platelet count maybe required due to issues with scheduling.
- h: To be performed at Visit 30 during Follow-up only:
- i: The sparse PK sample will be obtained at Visits 4, 7, 8, 13, and 22 (EOT).
- j: At Visits 5 and 10, one blood sample will be obtained pre-dose (trough), one sample between 2 and 4 hours post-dose, and another sample between 6 and 8 hours post-dose. Therefore, subjects should be instructed to take the study drug at the clinic during this visit, after collection of the pre-dose PK sample. These visits should be scheduled on a subject's regular dosing day. Serial sampling may need to occur at a visit later than Visit 5 or Visit 10 if study drug has been held or the dosing regimen has changed in the previous week. This is to ensure that the subject has been on a stable dose for at least 1 week when serial samples are collected.
- k: The pregnancy test will be performed at Week 20 and Week 34.

# APPENDIX B: EXTENSION PHASE SCHEDULE OF EVENTS

Visits a	E1 - 2	Е3	E4-5	E6	E7-8	E9	E10-11	E12	E13-14	E15	E16-17	E18	E19-20	E21	E22-23	E24 or EOT	Unsch Visit b
Months c	1-2	3	4-5	6	7-8	9	10-11	12	13-14	15	16-17	18	19-20	21	22-23	24 or EOT	
Concomitant medications	X	X	X	X	X	X	X	X	X	X	X	X	X	X	X	X	X
Vital signs	X	X	X	X	X	X	X	X	X	X	X	X	X	X	X	X	X
Physical examination	X		$X^d$		X d		X d		$X^{d}$		$X^d$		$X^d$		$X^{d}$	X	
Dispense study drug and diary, as needed	X	X	X	X	X	X	X	X	Х	X	Х	X	Х	X	X		
Retrieve unused study medication and record compliance	X	X	X	X	X	X	X	X	X	X	X	X	X	X	X	X	
Platelet counts	X	X	X	X	X	X	X	X	X	X	X	X	X	X	X	X	X
Chemistry/ Hematology/ Coagulation	X		X d		X d		X d		X d		X d		X d		X d	X	
Pregnancy Test	X		X d		X d		X d		X d		X d		$X^d$		X d	X	
Adverse Events	X	X	X	X	X	X	X	X	X	X	X	X	X	X	X	X	X
WHO Bleeding	X	X	X	X	X	X	X	X	X	X	X	X	X	X	X	X	X

EOT = end-of-treatment, Unsch = unscheduled, WHO = World Health Organization.

a: Subjects requiring study drug dose adjustments, undergoing concomitant ITP medication reduction or those who receive rescue therapy during the Extension Phase are required to return for weekly visits for 3 consecutive weeks.

b: This column details the minimum assessments required for those subjects who need an unscheduled visit for dose titration or additional platelet count blood draws, however additional assessment may be performed as required based on other reasons for the unscheduled visit.

c: Visits should occur within a +/- 7-day timeframe.

d: Physical exams, central labs and pregnancy tests will be performed every 3 months starting at Month 1 (Months 1, 4, 7, 10, 13, 16, 19, 22) and EOT.

# APPENDIX C: WHO BLEEDING SCALE

Grade 0	No bleeding
Grade 1	Petechial bleeding
Grade 2	Mild blood loss (clinically significant)
Grade 3	Gross blood loss
Grade 4	Debilitating blood loss

a: Fogarty, 2012; Miller, 1981

# APPENDIX D: MODERATE OR STRONG INDUCERS AND INHIBITORS OF BOTH CYP2C9 AND CYP3A4/5

**Note:** This list is not all-inclusive; it presents examples of common medications which are excluded during the study.

# **Dual Inducer examples**

- Carbamazepine
- Enzalutamide
- Rifampin/Rifampicin
- Phenytoin
- Phenobarbital

# **Dual Inhibitor examples**

- Fluconazole
- Ritonavir
- Grapefruit juice

| 13.2.4 | Treatment-emergent Adverse Events of Special Interest by AESI Category and PT | 36 |
| 13.2.5 | Treatment-emergent Adverse Events by SOC and PT by Subgroups | 36 |
| 13.2.6 | Treatment-emergent Adverse Events by PT | 37 |
| 13.2.7 | Treatment-emergent Adverse Events by SOC, PT and Maximum Severity..... | 37 |
| 13.2.8 | Treatment-emergent Adverse Events by Time to Onset and by PT | 37 |
| 13.3 | Laboratory Data | 38 |
| 13.3.1 | Laboratory Parameters and Change from Baseline by Visit..... | 39 |
| 13.3.2 | Laboratory Parameters with any Abnormal Measured Values by Visit | 39 |
| 13.4 | Vital Signs..... | 40 |
| 13.4.1 | Vital Signs Tests and Change from Baseline by Visit..... | 40 |
| 14 | Listings..... | 41 |
| 15 | References..... | 42 |
| 16 | Revision History | 42 |
| | Appendix 1: Sample Code..... | 42 |
| | Appendix 2: Tables of Background Factors for Demographics and Baseline Characteristics | 42 |
| | Appendix 3: Tables of Test Items of Laboratory Test, Vital Signs, and WHO Bleeding Scale... | 43 |
| | Table 1: List of Laboratory Test Items collected in Central Laboratory:..... | 43 |
| | Table 2: List of Vital Signs Test Items:..... | 44 |
| | Table 3: WHO Bleeding Scale: | 44 |

1 Abbreviations and Definition of Terms

| Abbreviation | Definition |
|--------------|--|
| AE | Adverse Event |
| AESI | Adverse Events of Special Interest |
| ATC | Anatomical Therapeutic Chemical |
| BLQ | Below Lower Limit of Quantitation |
| CI | Confidence Interval |
| CTCAE | Common Terminology Criteria for Adverse Events |
| CV | Coefficient of Variation |
| EOT | End-of-Treatment |
| FAS | Full Analysis Set |
| ITP | Immune Thrombocytopenia |
| IWG | International Working Group |
| MedDRA | Medical Dictionary for Regulatory Activities |
| PK | Pharmacokinetic(s) |
| PPS | Per-Protocol Set |
| PT | Preferred Term |
| SAE | Serious Adverse Event |
| SAF | Safety Set |
| SAP | Statistical Analysis Plan |
| SMQ | Standardised MedDRA Query |
| SOC | System Organ Class |
| TEAE | Treatment-emergent Adverse Event |
| TEAESI | Treatment-emergent Adverse Event of Special Interest |
| WHO | World Health Organization |

2 Introduction

This document is the Statistical Analysis Plan (SAP) containing definitions and descriptions of statistical analysis procedures for “An Open-label Study to Evaluate the Efficacy and Safety of Avatrombopag for the Treatment of Thrombocytopenia in Japanese Adults with Chronic Immune Thrombocytopenia (protocol number: AVA-ITP-307)”.

The SAP will be finalized, locked and signed prior to Core Phase database lock.

3 Study Objectives and Endpoints

3.1 Primary Investigation Phase (Core Phase)

3.1.1 Primary Objective

The primary objective of the Core Phase of this study is to evaluate the efficacy of avatrombopag in the treatment of Japanese adult subjects with immune thrombocytopenia (ITP), as measured by cumulative number of weeks of platelet response over 26 weeks.

3.1.2 Secondary Objectives

The secondary objectives are:

- To evaluate the platelet response rate at Day 8
- To evaluate the safety of avatrombopag in Japanese adult subjects with ITP

3.1.3 Exploratory Objectives

The exploratory objectives are:

- To evaluate the durable platelet response
- To evaluate the incidence of bleeding and use of rescue therapy
- To collect population PK data on plasma avatrombopag exposure in Japanese adult subjects with ITP

3.2 Extension Phase

3.2.1 Primary Objective

In the Extension Phase, the primary objective is to evaluate the safety and tolerability of long-term therapy with avatrombopag in Japanese subjects with chronic ITP.

3.2.2 Secondary Objective

The secondary objective in the Extension Phase is to evaluate the effectiveness of long-term therapy with avatrombopag as measured by platelet response, bleeding, and the use of rescue medication.

3.3 Study Endpoints

3.3.1 Primary Efficacy Endpoint

In the Primary Investigation Phase (Core Phase), the primary efficacy endpoint is the cumulative number of weeks in which the platelet count is $\geq 50 \times 10^9 / \text{L}$ during 26 weeks of treatment in the absence of rescue therapy.

Subjects using rescue therapy at any time during the 26-week treatment period will be considered not to have any platelet responses for all subsequent weeks after rescue therapy. A platelet response will be defined as a platelet count of $\geq 50 \times 10^9 / \text{L}$ and nonresponse will be defined as a platelet count $< 50 \times 10^9 / \text{L}$. All analyses of platelet counts will be based on local laboratory results.

Missing platelet assessments at any given time point will be considered a nonresponse at that time point. Subjects who discontinue the study or who are lost to follow-up before 26 weeks will have all subsequent unobserved scheduled platelet assessments at the scheduled time points as having “missing” platelet values.

3.3.2 Key Secondary Efficacy Endpoints

In the Primary Investigation Phase (Core Phase), the key secondary endpoint is the platelet response rate at Day 8 (as defined by the proportion of subjects with a platelet response $\geq 50 \times 10^9 / \text{L}$ at Day 8). Subjects with missing platelet count at Day 8 or use of rescue therapy before or on Day 8 will be considered platelet non-responders.

3.3.3 Other Secondary Efficacy Endpoints

Other efficacy endpoints in the Primary Investigation Phase (Core Phase) include the following:

- Durable platelet response as defined by proportion of subjects who have at least 6 of 8 (i.e., $\geq 75\%$) weekly platelet counts $\geq 50 \times 10^9 / \text{L}$ during the last 8 weeks of treatment over the 26-week treatment period in the absence of rescue therapy
- Incidence and severity of bleeding symptoms associated with ITP, including bleeding, bruising, and petechiae, measured using the World Health Organization (WHO) Bleeding Scale
- Maximum duration (in weeks) of continuous response for each subject
- Proportion of subjects receiving rescue therapy during the 26-week duration of the study

- Proportion of subjects with a reduction/discontinuation in use of concomitant ITP medications from baseline
- Complete responder by International Working Group (IWG) definition: platelet count $\geq 100 \times 10^9 / \text{L}$ and absence of bleeding
- Responder by IWG definition: platelet count $\geq 30 \times 10^9 / \text{L}$ and at least a 2-fold increase in baseline count and absence of bleeding

Additionally, in the Extension Phase, effectiveness will be assessed by measuring platelet counts, rescue therapy uses, and bleeding events. Specifically,

- Median platelet count of all subjects at selected time points (monthly)
- Proportion of subjects needing rescue therapy
- Incidence and severity of bleeding (in accordance with the WHO Bleeding Scale)

4 Study Methods

4.1 Overall Study Design and Plan

This confirmatory, open-label study will evaluate the efficacy, safety, and PK of avatrombopag in Japanese adults with ITP. While a placebo control group was included in the pivotal avatrombopag overseas study, the mean number of cumulative weeks with a platelet response in this group was zero (0), a result which is consistent with placebo control groups in other ITP studies. Therefore, inclusion of a placebo control group in this study would not be expected to be informative. To compare this study's data to the data from the pivotal Study 302, the study design (other than not including a placebo control) will replicate that of the overseas study. Avatrombopag will be evaluated over a duration of 26 weeks and the primary efficacy endpoint will be the cumulative number of weeks of platelet response $\geq 50 \times 10^9 / \text{L}$. All subjects who complete the Primary Investigation Phase (Core Phase) can continue to receive avatrombopag in the Extension Phase until market authorization in Japan. Safety and efficacy data will be collected monthly in the Extension Phase.

4.2 Selection of Study Population

This study will enroll at least 19 Japanese adults with chronic ITP (≥ 12 months duration) and an average of 2 platelet counts $< 30 \times 10^9 / \text{L}$, who meet all eligibility criteria.

4.3 Randomization and Blinding

All subjects enrolled in this study will receive open-label avatrombopag. Therefore, no randomization or blinding is required.

5 Sequence of Planned Analysis

5.1 Changes from Planned Analyses in the Protocol

A secondary efficacy endpoint was included which was not detailed in the protocol: Proportion of subjects with a reduction in use of concomitant ITP medications from baseline.

Bleeding Adverse Events of Special Interest (AESIs) were first identified using a Standardised Medical Dictionary for Regulatory Activities Query (MedDRA SMQ) and then further defined as clinically significant using reported Common Terminology Criteria for Adverse Events (CTCAE) grade for the event rather than the WHO bleeding grade, as WHO bleeding grades collected at study visits are not linked to specific adverse events.

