# 9.1.2 Adverse Events of Special Interest

The Investigator will monitor each subject for clinical and laboratory evidence for pre-defined AEs of special interest (AESI) throughout their participation in this study. The purpose for specifying these AESI is to enable further characterization of the clinical course and management of these events. An AESI may or may not be the consequence of treatment with avatrombopag.

The AESI defined in this protocol include:

- Thromboembolic events (any thrombotic or embolic event, whether arterial or venous); and
- Bleeding events (WHO Grades 3 and 4).

These events will be recorded in the AE eCRF page. The Investigator will assess and record any additional information on the AESI in detail on a SAE form (whether or not the event meets seriousness criteria in Section 9.3), to be submitted within 24 hours of awareness of the event. During the course of the study, additional AESI may be identified by the Sponsor.

Efficacy endpoints, as described in Section 3, should not be reported as AEs unless in the opinion of the Investigator the event is causally associated with the study drug. For example, thrombocytopenia or platelet transfusions for thrombocytopenia should not be reported as AEs; however, clinically significant bleeding events should always be reported as AESIs.

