#### 11 DATA MANAGEMENT AND RECORD KEEPING

# 11.1 Data Management

# 11.1.1 Data Handling

Data will be recorded at the site on eCRFs and reviewed by the clinical research associate (CRA) on an ongoing basis and during monitoring visits. The CRAs will verify data recorded in the electronic data capture (EDC) system with source documents. All corrections or changes made to any study data must be appropriately tracked in an audit trail in the EDC system. An eCRF will be considered complete when all missing, incorrect, and/or inconsistent data has been accounted for and reconciliation between other databases (e.g., safety) is complete.

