| TEAE of Special Interest (TEAESI)/Related TEAESI | 
TEAE of Special Interest (TEAESI) is a treatment-emergent adverse event which meets the following descriptions:
 
 - Thromboembolic events include the adverse events with MedDRA PT belonging to Standard MedDRA Queries (SMQ Narrow PTs) 'Embolic and thrombotic events'. - Bleeding events include the adverse events with MedDRA PT belonging to 2nd level SMQ (Narrow PTs) 'Haemorrhage terms (excl laboratory terms)' with CTCAE Grades 3 and 4. 
A related TEAESI is a TEAESI whose Investigator causality assessment is related.
 |
| Adverse Event Severity | 
The severity of all AEs should be graded according to the Common Terminology Criteria for Adverse Events Version 5.0 (CTCAE). For those AEs not listed in the CTCAE, the following grading system should be used:
 
 - Mild (CTCAE Grade 1): Transient symptoms, awareness of sign/symptom, but easily tolerated and no interference with subject's daily activities. - Moderate (CTCAE Grade 2): Marked signs/symptoms that interfere with subject's usual activities, but still acceptable. - Severe (CTCAE Grade 3): Incapacitating signs/symptoms which cause considerable interference with the subject's daily activities, unacceptable. - Life-threatening (CTCAE Grade 4): Life-threatening or disabling AE. - Death (CTCAE Grade 5): Death-related AE. |

The data handling methods for Adverse Events are presented below:

Only TEAEs will be tabulated in the tables. Non-TEAEs are only included in the listings.

- Number of Subjects with Multiple Events:
- For overview summary:
 - If multiple AEs occurred in the same subject, the subject will only be counted once.

- If AEs with multiple grades occurred in the same subject, the subject will be counted once in the highest reported grade.
- For summary by SOC and PT:
 - If multiple AEs of same SOC or PT occurred in the same subject, the subject will only be counted once in the SOC or PT.
 - If multiple AEs of same SOC or PT with different grades occurred in the same subject, the subject will be counted once in the highest reported grade.
- For summary by PT:
 - If multiple AEs of same PT occurred in the same subject, the subject will only be counted once in the PT.
- For summary by AESI category and PT:
 - If multiple AEs of same AESI category or PT occurred in the same subject, the subject will only be counted once in the AESI category or PT.

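### The bleeding-AESI outputs count only narrow-SMQ terms with CTCAE Grade 3 or 4, so a bleed that a site reported as an AESI under the protocol can be left out of them

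*SAP*

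**What the plan says.** Protocol 9.1.2 lists as an AESI "Bleeding events (WHO Grades 3 and 4"). On recording, it says "These events will be recorded in the AE eCRF page" and "The Investigator will assess and record any additional information on the AESI in detail on a SAE form", within 24 hours and whether or not the event is serious. The same section adds that "clinically significant bleeding events should always be reported as AESIs". Protocol 9.1.1.1 has every AE graded by CTCAE version 5.0, a separate scale.

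SAP 5.1 declares a departure from the protocol. Bleeding AESIs are found by a MedDRA query and then restricted by CTCAE grade instead of WHO grade, "as WHO bleeding grades collected at study visits are not linked to specific adverse events". SAP 13.2 puts this into effect: "Bleeding events include the adverse events with MedDRA PT belonging to 2nd level SMQ (Narrow PTs") for haemorrhage, and only with CTCAE Grade 3 or 4. That definition governs the overview (13.2.1), its subgroups (13.2.2), the AESI table (13.2.4) and, by its title, listing 14.3.2.3. No section of the SAP adds events that the Investigator reported as AESIs.

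**The concern.** The SAP's reason is sound for what it addresses: a WHO score taken at a visit describes the subject since the last visit and belongs to no particular AE. It does not address the AESI reports. Under Protocol 9.1.2 those are made event by event, so using the site's designation needs no link to a visit score. The SAP does not say why the designation is set aside.

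Safety is a secondary objective of the Core Phase and the primary objective of the Extension Phase. A reader of the AESI table will expect it to hold the events that sites were told to report as AESIs. As defined, it need not.

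**Working it through.** No stated figure is in dispute, so the check compares the two rules. Inputs: the AESI definition and recording rule (Protocol 9.1.2), AE severity grading (Protocol 9.1.1.1), the WHO scale (Protocol Appendix C) and the TEAESI definition (SAP 13.2). Each row below is a treatment-emergent bleed.

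| Event | AESI by Protocol 9.1.2 grade? | Counted by SAP 13.2? |
|---|---|---|
| WHO 3–4, CTCAE 3–4, term in the narrow SMQ | Yes | Yes |
| WHO 3–4, CTCAE 1–2, term in the narrow SMQ | Yes | No |
| WHO 3–4, any CTCAE grade, term outside the narrow SMQ | Yes | No |
| WHO 3–4, fatal (CTCAE 5), term in the narrow SMQ | Yes | No, read literally |
| WHO 1–2, CTCAE 3–4, term in the narrow SMQ | No | Yes |

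The second row is possible because neither document maps one scale to the other. The fourth follows because the SAP stops at Grade 4, although Grade 5 is one of its own severity categories. The fifth row shows that the rule can also add events.

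The protocol side is itself unclear at one point. Section 9.1.2 sets the AESI threshold at WHO Grade 3 but also requires clinically significant bleeds to be reported as AESIs. Appendix C words Grade 2 as "Mild blood loss (clinically significant"). Site reports may therefore include Grade 2 bleeds.

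Scale, assuming a Safety Set of 19 (the planned sample size):

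- One subject contributes 1/19 = 5.3 percentage points.
- Restoring one omitted subject to an otherwise empty row moves it from 0/19 (0.0%, exact 95% CI 0 to 17.6%) to 1/19 (5.3%, exact 95% CI 0.1 to 26.0%).

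The documents give neither a rate of WHO Grade 3–4 bleeds nor a rate of disagreement between the scales. For illustration only, let r be an assumed proportion of subjects with a WHO Grade 3–4 bleed and d an assumed proportion of those graded CTCAE 1–2. The chance of at least one omitted subject is 1 − (1 − r·d)^19:

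- r = 2%, d = 10%: 1 − 0.998^19 = 3.7%
- r = 5%, d = 25%: 1 − 0.9875^19 = 21.3%
- r = 10%, d = 50%: 1 − 0.95^19 = 62.3%

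The width of that range reflects the assumptions, not evidence from the trial.

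**The case against.** The strongest reply is that this is a declared choice. SAP 5.1 states the change with a reason, the SAP is to be locked before the Core Phase database lock, and CTCAE is the scale the protocol requires for every AE. All of that stands, and this is not a hidden discrepancy. It does not explain why the site's own AESI reports go unused.

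The next reply is that the information is reported elsewhere, and largely it is. A treatment-emergent bleed appears in SAP 13.2.3, 13.2.6 and 13.2.7 and in AE listing 16.2.7. A serious one is also in listing 14.3.2.2, and a fatal one in the outputs for TEAEs leading to death. Visit WHO grades are in table 11.3.11 and listing 16.2.6.3. A reader might infer that such a bleed vanishes from the report; it does not. Table 11.3.11 is still no replacement for the AESI rows: it shows one worst grade per subject, is not tied to AEs, and for the Core Phase excludes tapering and follow-up.

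Three further inferences are tempting and not supported:

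- That the two scales differ because CTCAE grades interference with daily activities. That wording is only the fallback for AEs not listed in CTCAE, and no bleeding term is shown to fall under it. The point rests on the missing mapping.
- That thromboembolic AESIs have the same defect. Their SAP definition has no grade filter, and no thrombotic term is shown to fall outside the query.
- That an AESI flag exists and is already reconciled. No section describes an AESI flag or an event-level WHO grade, and the same SAE form serves SAEs and AESIs. Protocol 11.1.1 requires only in general terms that "reconciliation between other databases (e.g., safety) is complete".

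**Conclusion.** The point holds within limits. The SAP's definition can leave a protocol-defined, site-reported bleeding AESI out of 13.2.1, 13.2.2, 13.2.4 and listing 14.3.2.3, and read literally it leaves out a Grade 5 bleed. The reason given in SAP 5.1 does not cover this.

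A reader might go further and conclude that serious bleeding is understated overall. The documents do not show that. The effect is confined to the AESI outputs, the rule can also add events, and the frequency of disagreement is unknown, so the net direction is open. The only firm size is 5.3 percentage points per subject, on the assumption of 19 in the Safety Set. No primary or key secondary efficacy result is affected. This is an inexpensive improvement to the safety reporting.

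**What to change.** 1. In SAP 13.2, keep the SMQ/CTCAE search but set its grade condition to CTCAE Grade 3 or higher, and change the labels in 13.2.1, 13.2.2 and 13.2.4 to match.
2. In 13.2.1, 13.2.4 and listing 14.3.2.3, add a separately labelled row or category for TEAEs that the Investigator reported as AESIs. Identify them from an AESI flag if there is one, otherwise by matching AE records to the AESI/SAE forms. Show each event's source and its available grade or grades.
3. Record both changes in SAP 5.1.
4. Reconcile the two statements in Protocol 9.1.2 on which bleeds are AESIs with the Grade 2 wording in Appendix C, and state in the SAP how site-reported Grade 2 bleeds will be shown.

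The cost is SAP wording, some record matching in a study of about 19 subjects, and a footnote for events whose sources or grades differ. The sponsor's own search remains visible as a separate row.
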